4 SUBJECT SELECTION

4.1 Subject Recruitment

4.1.1 Inclusion Criteria

- 1. Adult surgical patients (≥18 years of age)
- 2. Non-cardiac surgery
- 3. Non-major neurologic surgery (e.g., non-intracranial, non-major spine)
- 4. Non-major vascular surgery (i.e., below the diaphragm)

4.1.2 Exclusion Criteria

- 1. Emergency surgery
- 2. Severe cognitive impairment precluding capacity for informed consent
- 3. Uncontrolled cardiac arrhythmias
- 4. Seizure disorder history
- 5. Intolerance or allergy to caffeine
- 6. Preoperative opioid use
- 7. Pheochromocytoma
- 8. Enrolled in conflicting research study
- 9. Patients in acute liver failure
- 10. Pregnancy
- 11. Breastfeeding
- 12. Severe audiovisual impairment
- 13. Non-English speaking

5 STUDY TREATMENTS

5.1 Allocation to Treatment

Participants will be block randomized with a 1:1 allocation ratio (placebo: caffeine) in a two-arm parallel design, and the randomization schedule and coding will be held by our hospital research pharmacy. Prepared intravenous piggyback solutions of 5% dextrose in water (placebo) or caffeine citrate (200 mg caffeine) will be directly delivered to the operating room prior to the surgery of enrolled participants.

5.2 Breaking the Blind

The randomization can be broken, if necessary, per the physicians caring for the subject to ensure subject safety. With the exception medical emergency, the blind will only be broken by the PI.

5.3 Drug Supplies

5.3.1 Formulation, Preparation and Dispensing

Parenteral drug products should and will be inspected visually for particulate matter prior to administration whenever solution and container permit. Per manufacturer (Fresenius Kabi USA, LLC) package insert: Caffeine citrate injection is indicated for the short-term treatment of apnea of prematurity in infants between 28 and < 33 weeks gestational age.

Caffeine citrate injection, USP for intravenous administration is a clear, colorless, sterile, nonpyrogenic, preservative-free, aqueous solution adjusted to pH 4.7. Each mL contains 20 mg caffeine citrate (equivalent to 10 mg of caffeine base) prepared in solution by the addition of 10 mg caffeine anhydrous to 5 mg citric acid monohydrate, 8.3 mg sodium citrate dihydrate and Water for Injection. Caffeine, a central nervous system stimulant, is an odorless white crystalline powder or granule, with a bitter taste. It is sparingly soluble in water and ethanol at room temperature. The chemical name of caffeine is 3,7-dihydro-1,3,7-trimethyl-1*H*-purine-2,6-dione. In the presence of citric acid it forms caffeine citrate salt in solution.

Caffeine citrate is supplied via vials that contain 3mL of solution at a concentration of 20 mg/mL caffeine citrate (60 mg/vial) equivalent to 10 mg/mL caffeine base (30 mg/vial).

5.3.2 Drug Storage and Drug Accountability

Caffeine citrate injection, USP (NDC 63323-407-03), is stored at 20-25 degrees Celsius (68-77 degrees Fahrenheit) in 3 mL single-dose vials. The drug will be stored in the hospital research pharmacy in accordance with hospital pharmacy practice and guidelines.

5.4 Concomitant medications

No other study drugs will be given. Participants will receive medications as clinically indicated by perioperative providers.

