2.2 Endpoints

2.2.1 Primary Endpoint

Cumulative opioid consumption (mg) through postoperative day 3 (or discharge, whichever is sooner.

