3 STUDY DESIGN

This will be a single-center, triple-blinded, randomized controlled trial at the University of Michigan Health System, and approval has been obtained from the University Michigan Medical School IRB. The overall study flow is presented in the CONSORT⁴¹ Flow Diagram (Figure 2). As with our past studies, patients will be recruited at preoperative clinics, where informed consent will be obtained. Randomization methods will follow a stratified randomization model to match patients based on age and gender. Participants will be randomized with a 1:1 allocation ratio (placebo: caffeine) in a two-arm parallel design, and the randomization schedule and coding will be held by our hospital research pharmacy. Prepared intravenous piggyback solutions of 5% dextrose in water or caffeine citrate (200 mg caffeine) will be directly delivered to the operating room prior to the surgery of enrolled participants. The dose of 200 mg was chosen for two reasons: (1) this dose is in-line with similar clinical neurophysiology studies involving caffeine^{34,35,42,43} and (2) this has been the intraoperative dose used for safely preventing post-dural puncture/post-operative pain in surgical and obstetric patients. ^{22,29,32} In these studies, no significant side effects or adverse events were reported in relation to caffeine. This study will fulfill CONSORT guidelines⁴¹ for clinical trials as outlined in the following sections. Furthermore, this trial will be registered with www.clinicaltrials.gov prior to trial initiation, and all study team members will be certified in Good Clinical Practice as outlined by the NIH.

Assessment for **Enrollment** eligibility **Exclusions** Randomization Allocation Allocation to placebo (n=30) Allocation to caffeine (n=30) Analysis Analysis Anesthetic emergence time ◆ Anesthetic emergence time ◆ EEG power and connectivity · EEG power and connectivity ◆ Trail Making Test ◆ Trail Making Test · Postoperative opioid use Postoperative opioid use • Postoperative pain assessments · Postoperative pain assessments Delirium assessments · Delirium assessments Depression, anxiety scales • Depression, anxiety scales ◆ Affect questionnaire ◆ Affect questionnaire ◆ 30-day follow-up health survey ◆ 30-day follow-up health survey

Figure 2: Planned study flow diagram based on Consolidated Standards of Reporting Trials (CONSORT)

Planned study flow diagram based on Consolidated Standards of Reporting Trials (CONSORT).⁴¹ EEG = electroencephalogram

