Inclusion criteria: Adult (≥18 years old) patients undergoing non-cardiac, non-neurologic, non-major vascular surgery (i.e., below the diaphragm).

Exclusion criteria: Emergency surgery, cognitive impairment precluding capacity for informed consent, uncontrolled cardiac arrhythmias, seizure disorders, intolerance or allergy to caffeine, history of diabetes, preoperative opioid use, pheochromocytoma, acute liver failure, enrolled in conflicting research study, pregnancy, breastfeeding, severe visual or auditory impairment (may hinder cognitive function testing), and patients unable to speak English.

Perioperative and anesthetic procedures: Patients will be consented and enrolled at preoperative clinic locations, where a medical and psychiatric history will be taken and baseline assessments will be administered (described further below). After enrollment, patients will also complete a caffeine intake survey to quantify baseline caffeine consumption. On the day of surgery, baseline cognitive function testing (TMT) will take place in the preoperative holding area. Subsequently a 16-channel wireless EEG system (Cognionics, Inc.) will be applied to the scalp for continuous monitoring during surgery and the perioperative period. Once in the operating room, anesthetic induction and maintenance will proceed as deemed clinically appropriate by the anesthesia team. At the beginning of surgical closure, the study drug will be given via intravenous infusion over 60 minutes (placebo vs. caffeine, 200 mg) in a triple-blinded fashion: the anesthetic team, research staff, and patient will all be blinded to the intervention. Infusion of this dose over a 60-minute period has been safely described, without significant side effects or adverse events noted.^{28,32} A member of the research team will remain in the operating room to monitor drug infusion and collect data regarding timing of anesthetic discontinuation and emergence; this will aid methodological rigor and data validation for the study. The EEG sensors will remain in place during the operation and emergence from anesthesia; they will then be removed shortly after PACU arrival. One hour after the caffeine infusion finishes, pain and cognitive function measures will be assessed.

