9 DATA ANALYSIS/STATISTICAL METHODS

9.1 Sample Size Determination

Sample size and power analysis is based on opioid consumption data observed in 102 hysterectomy patients treated at the University of Michigan with patient heterogeneity with respect to CNS involvement in the pain processing summarized by the Fibromialgia Survey score (FM). Acute opioid responses on POD1 varied between 0.7 and 6.5 (mean OME) with the standard deviation varying 3-18, dependent on the tertile of the FM score. Based on these data we hypothesize that caffeine affecting the pain processing system can show a difference as large as 0.7 vs. 6.5 with standard deviations of 3 and 10, respectively. This will give us the power of 83%, with a sample size of 60, to detect the difference by a two-sided ttest with unequal variances. We note that the opioid consumption distribution is of exponential type and therefore sample means, while approximately normal are a rather crude summary of the difference in the OME distribution by group. We therefore consider the above calculation conservative. The expected reserves of power attained through the use of the appropriate longitudinal model (see Analysis of Primary Endpoint) will be used to lend more power to secondary regression and causal analyses involving explanatory variables and potential mediators. We expect a ~10% drop-out rate, and will continue recruitment until the full 71 patients have been recruited (after drop-out).

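### The regression for cumulative opioid use fixes no covariate for operation or planned regional technique, which costs precision and leaves the adjustment set to the data

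*Combined protocol and SAP*

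**What the plan says.** The primary endpoint in Section 2.2.1 is "Cumulative opioid consumption (mg) through postoperative day 3 (or discharge, whichever is sooner". Section 3 enrols "Adult (≥18 years old) patients undergoing non-cardiac, non-neurologic, non-major vascular surgery". Section 4.1 excludes cardiac, major neurologic, major vascular and emergency operations, as well as patients already using opioids, but otherwise does not restrict the procedure.

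Background analgesia is open. Section 3 states that "anesthetic induction and maintenance will proceed as deemed clinically appropriate by the anesthesia team", and Section 5.4 that "Participants will receive medications as clinically indicated by perioperative providers". No section limits regional, neuraxial or non-opioid analgesia, and none plans to tabulate it. Intraoperative opioid is to be compared between groups (Section 3).

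On balance, Section 3 says "Randomization methods will follow a stratified randomization model to match patients based on age and gender". Section 5.1 mentions blocks only and names no strata.

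On analysis, Section 9.2.3 assigns linear regression to the cumulative endpoint and lists no covariates. Further models add demographics and then intraoperative factors, which are not itemised. The reported model is chosen by likelihood-ratio tests and AIC. Section 9.2.2 also admits to the multivariable models any measure whose standardized difference exceeds 0.1.

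The planning figures in Section 9.1 rest on "opioid consumption data observed in 102 hysterectomy patients", that is, on one procedure. They assume that caffeine "can show a difference as large as 0.7 vs. 6.5 with standard deviations of 3 and 10, respectively".

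**The concern.** The operation performed, and whether a regional or neuraxial technique was planned, can be expected to predict how much opioid a patient uses. Both can be known before randomisation, since the Schedule of Activities puts randomisation on the day of surgery. Leaving such predictors out of a regression on opioid use leaves their variance in the residual.

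The plan does have routes by which they could enter, but each is settled after the data are seen. The analyst decides what counts as an intraoperative factor, AIC decides which model is reported, and the 0.1 screen responds mostly to chance at this sample size. Two competent analysts could follow the plan and report different adjusted estimates. At stake are power in a trial of about 60 patients and the credibility of whichever estimate is reported.

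**Working it through.** **Inputs.** From Section 9.1: means 0.7 and 6.5 (difference 5.8), SDs 3 and 10, N = 60, two-sided unequal-variance t-test, stated power 83%. From Section 3: 1:1 allocation, 30 per arm in the flow diagram. Alpha is not stated, so 0.05 is assumed. The documents give no effect of operation or block on opioid use, so every effect size and R² below is an assumption.

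**1. The plan's own figure.** SE = √(3²/30 + 10²/30) = √(109/30) = 1.906. Noncentrality = 5.8/1.906 = 3.04, with 34.2 Satterthwaite degrees of freedom. Power from the noncentral t is 84.0%, which agrees with the stated 83%. The root-mean-square SD is √(109/2) = 7.38, so the planned effect is 5.8/7.38 = 0.79 SD.

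**2. A strong predictor left out, with its variance added to the stated SDs.** Assume a block lowers opioid use by 0.8 SD: 0.8 × 7.38 = 5.9 mg. If used in a proportion p of patients, it adds 5.9² × p(1 − p) to each arm's variance.
- p = 0.3: adds 7.3. SE = √((9 + 7.3 + 100 + 7.3)/30) = 2.03, power 79%.
- p = 0.5: adds 8.7. SE = √((9 + 8.7 + 100 + 8.7)/30) = 2.05, power 79%.

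**3. Predictors prespecified, with their variance already inside the stated SDs.** Multiply both SDs by √(1 − R²) and repeat step 1, ignoring the two or three degrees of freedom spent.

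| R² (assumed) | Power |
|---|---|
| 0 | 84% |
| 0.10 | 88% |
| 0.20 | 91% |
| 0.30 | 94% |
| 0.40 | 97% |

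**4. Is there bias?** In 20,000 simulated trials per setting with no caffeine effect, a factor present in 30% or 50% of patients lowered opioid use by 5, 10 or 20 mg and was left unadjusted. The Welch test rejected in 4.7% to 5.3% of runs.

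**5. How large is chance imbalance?** By exact binomial calculation at 30 per arm, with use of 30-50%, the arms differ by at least 20 percentage points in 12-16% of trials. With the 0.8 SD block, such an imbalance moves the contrast by 0.20 × 0.8 = 0.16 SD. The standard error of the contrast is √(2/30) = 0.26 SD, so the shift is 0.16/0.26 = 0.62 standard errors.

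**6. What does the 0.1 screen detect?** Take a binary factor with the same expected frequency in both arms. The exact probability that its standardized difference exceeds 0.1 at 30 per arm is 65%, 67% and 70% at frequencies of 20%, 30% and 50%. For a continuous covariate it is 2 × (1 − Φ(0.1/√(2/30))) = 70%. A split of 8 against 10 out of 30 is enough: 0.067/√((0.196 + 0.222)/2) = 0.15.

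**The case against.** A reader might infer that uncontrolled background analgesia could mimic a caffeine effect. The documents do not support that as a bias claim. Allocation is randomised ("Participants will be randomized with a 1:1 allocation ratio (placebo: caffeine) in a two-arm parallel design") and the anaesthetic team, research staff and patient are blinded. Chance imbalance is therefore part of the sampling error that alpha and the confidence interval already cover, as steps 4 and 5 show.

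Two other strong readings also fail. Eligibility does not extend to any surgery: several classes are excluded, and Section 9.2.1 describes the population as major surgery. Nor is it right that similarity of background analgesia between arms could never be shown. Section 9.2.2 relies on inpatient medication administration records for the primary outcome, and the same records can supply non-opioid use. What is missing is a plan to extract and report it.

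The defence has further points. Mixed surgery under usual-care analgesia is a legitimate choice in a Phase II trial whose synopsis states a feasibility objective. Adjustment is partly foreseen, and because study drug starts only at surgical closure, analgesia given before then precedes treatment and may validly be adjusted for. The power loss in step 2 is modest. Section 9.1 gives no SD for a mixed surgical population and reports SDs from 3 to 18 within hysterectomy alone, so the loss relative to a single procedure cannot be quantified from the documents.

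All of this limits the size and kind of the problem. It does not answer the narrower point: the covariates are not named, and the stated rules for choosing them depend on the data and, in the case of the 0.1 screen, largely on chance.

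**Conclusion.** The point holds as one of precision and prespecification. For an endpoint made of opioid use, two strong candidate predictors that can be known before randomisation are left to post hoc selection.

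The size depends on assumptions: two-sided alpha of 0.05, 30 analysed per arm, the planning means and SDs as stated, and illustrative effects of block and procedure. Under them, omission costs about 5 points of power (84% to about 79%) for a 0.8 SD block. Naming the covariates gains about 4 to 13 points (to 88-97%) if they explain 10-40% of the variance already in the planning SDs. The finding on the 0.1 screen needs no assumed effect size: about two thirds of null factors pass it.

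This is a cheap improvement, not a threat to the validity of the randomised comparison.

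**What to change.** In Section 9.2.3, define the primary model for cumulative opioid use as linear regression on treatment arm with two fixed covariates: procedure class (for example laparoscopic, open abdominal, other) and planned regional or neuraxial technique (yes/no). Record both before randomisation. State that they stay in the model whatever the 0.1 screen, likelihood-ratio tests or AIC indicate, and label any model chosen by those rules as supplementary.

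Tabulate postoperative inpatient non-opioid analgesics by arm from the medication administration record. Do not adjust for them, because they follow study drug and could be affected by it.

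The cost is two or three model degrees of freedom, two items recorded at baseline, and a small extraction from a record already in use. No stratification factor need be added: planned technique on top of age and gender would give 2 × 2 × 2 = 8 strata if each has two levels, an average of 60/8 = 7.5 patients per stratum, and fixed covariates recover most of the precision without that. Clinical care does not change.

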6 STUDY PROCEDURES

6.1 Screening Visit

For initial screening visits, patients will be seen during preoperative clinic visits. The study coordinator will review the study details with potential participants, and informed consent will be obtained after confirming eligibility criteria are met. Depending on when a preoperative clinic visit is scheduled in relation to surgery, the timeframe from enrollment to drug administration may vary significantly (days-to-weeks). The goal will be to recruit patients whose surgeries are scheduled for the morning, so as to minimize the likelihood of administering caffeine late in the afternoon. See "Schedule of Activities" for full list of procedures that will occur at this visit and all subsequent visits. Assessments, testing, and measures are described in detail in the above "Study Design" section.

6.2 Treatment Study Period

6.2.1 Visit 1 (Day 1)

As outlined in the above protocol, visit 1 (day 1) will be the day of scheduled surgery. During this time, a preoperative pregnancy test will first be drawn as clinically indicated. Vitals will be taken throughout the perioperative period per clinical guidelines and protocols. The RCSQ will be administered to assess sleep quality the prior evening. Baseline Trail Making Test (TMT) scores will be collected. The wireless EEG cap will then be placed preoperatively, and EEG monitoring will then commence perioperatively under supervision of the study team. A member of the study team will then receive the study drug from the research pharmacy, which will prepare the drug per block randomization protocol. The study team will then administer this during (one-hour infusion) at the beginning of surgical closure. The EEG cap will be removed after postanesthesia care unit (PACU) arrival, and one hour after the infusion has finished, the study team will perform the designated research study assessments (i.e., pain assessments, cognitive function testing, and Quality of Recovery (QoR) questionnaire). Intraoperative and PACU opioid data will also be tabulated.

6.2.2 Visits 2 – 4 (Postoperative Days 1-3)

Morning and afternoon pain (VAS, BPS), delirium, sleep disturbance, and caffeine intake assessments will be taken. Opioid consumption will be calculated during this time, and adverse events will also be recorded. Vitals will be recorded per clinical protocol on each respective ward/ICU. On postoperative day one, QoR will be collected. On postoperative day three, follow-up inpatient HADS and PANAS assessments will take place to assess depression, anxiety, and affect.

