2.2.2 Secondary Endpoint*

- VAS, n, PACU and postoperative days 1-3 (twice daily)
- BPS, n, PACU and postoperative days 1-3 (twice daily)
- Time until anesthetic emergence (min)
- Delirium incidence (%)
- Positive depression screen incidence (%)
- Positive anxiety screen incidence (%)
- Change in affect scores (n)
- Change in Trail Making Test scores (n) from baseline

^{*}Tertiary assessments are listed in section 7.2

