Neurocognitive assessments: Time from surgical closure to anesthetic emergence will be calculated by the study team. (minutes). The Trail Making Test will be used to assess perioperative cognitive function. The TMT is a validated, reliable test that assesses four cognitive domains relevant to the perioperative setting: processing speed, attention, visual scanning, executive function, and working memory. The TMT is administered in a standardized fashion using paper and pencil and takes approximately 5 minutes to complete. This is a feasible strategy in the perioperative setting to obtain comprehensive cognitive function data (e.g., attention, executive function) in a relatively short period of time, and normalized population data are available for comparisons. The test will be administered preoperatively and one hour after the caffeine infusion has completed in conjunction with pain assessments. Changes (n) in standardized scores from baseline will be calculated, and final standardized scores (n) will also be calculated and reported in the event that baseline scores are unable to be obtained (given the time-constraints present in the preoperative setting, it might not be possible to achieve baseline cognitive function scores in all patients).

Neuropsychological assessments: The Hospital Anxiety and Depression Scale (HADS)³⁸ will be used to assess for active depression and anxiety symptoms in each group. These assessments will take place at baseline and after the last inpatient assessment on postoperative day 3. Scores ≥8 for the anxiety (HADS-A) and depression (HADS-D) subscales will be considered positive screens.⁵¹ The Positive and Negative Affect Schedule

(PANAS)³⁹ will be used to characterize mood and affect at the same time points as depression and anxiety screening (baseline and postoperative day 3). The *Confusion Assessment Method (CAM)* will be used to assess for delirium throughout the first three postoperative days using previously described methods.^{14,40} Lastly, a follow-up health and well-being survey will be sent to participants thirty days after surgery. This survey will include the Veterans RAND 12 Item Health Survey (VR-12, continuous measure).⁵² Presence of persistent opioid use (yes/no, binary) will also be asked in this thirty-day survey.

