6.2.3 Follow-up (Postoperative Days 4-7)

During this time, opioid consumption and caffeine intake assessments will be obtained over the telephone. Adverse events will continue to be monitored.

SCHEDULE OF ACTIVITIES

	Screen	Visit 1 Day 1	Visit 2 Day 2	Visit 3 Day 3	Visit 4 Day 4	Phone call Days 5-7	Day 30
Protocol Activity		Day of Surgery	POD1	POD2	POD3	POD4-7	
Visit (POD1-3) /Phone call (POD4-7)	-	X	X	X	X	X	
Informed consent	X						
Medical history	X						
Vitals*	X	X	X	X	X		
Depression, Anxiety, and Affect Scales	X			X			
Serum pregnancy test		X					
Randomization		X					
Treatment with study agent		X					
Opioid use assessments		X	X	X	X	X	
Cognitive function testing	X	X^{\dagger}					
Pain/sleep assessments [‡]	X	X	X	X	X		
Caffeine intake assessment	X		X	X	X	X	
EEG assessments		X			·		
Adverse event assessment	_	X	X	X	X	X	
Health and well-being survey							X

^{*} Vitals will be recorded per clinical protocol on each respective ward/ICU. †Second cognitive function testing session will occur in the postanesthesia care unit ‡Pain and sleep assessments will occur and twice daily (morning and afternoon) from POD1-3; the RCSQ in particular will be administered on Day 1, preoperatively. Pain assessments will also be taken once in the postanesthesia care unit prior to the cognitive function assessment. POD = postoperative day, TMT = trail making test, EEG = electroencephalogram

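### Follow-up HADS and PANAS are planned only as an inpatient POD3 assessment, so three secondary endpoints have no planned route of collection in patients discharged earlier

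*Combined protocol and SAP*

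**What the plan says.** All references are to the combined protocol and SAP.

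- **Timing and setting.** Section 6.2.2 states that on POD3 "follow-up inpatient HADS and PANAS assessments will take place to assess depression, anxiety, and affect". Section 3 (Neuropsychological assessments) says of HADS: "These assessments will take place at baseline and after the last inpatient assessment on postoperative day 3". It places PANAS "at the same time points as depression and anxiety screening (baseline and postoperative day 3").
- **Endpoints that depend on this visit.** Section 2.2.2 lists eight secondary endpoints. Three need the follow-up scales: "Positive depression screen incidence", the matching anxiety screen, and change in affect scores.
- **Early discharge is foreseen.** Section 2.2.1 counts opioid consumption "through postoperative day 3 (or discharge, whichever is sooner"), and section 3 (Pain and sleep assessments) repeats that limit. Section 4.1.1 sets no minimum stay.
- **Later contacts.** In section 6.2.3, "opioid consumption and caffeine intake assessments will be obtained over the telephone" on POD4-7, with continued adverse event monitoring. The day-30 survey in section 3 covers VR-12 and persistent opioid use. Neither contact includes HADS or PANAS.
- **Missing data.** Section 9.2.2 considers complete-case analysis when data are MAR and under 20% are missing. Above 20% it calls for multiple imputation using the analysis variables and auxiliary variables. Discharge is not mentioned as a cause of missing scores. Section 9.2.4 plans two-group tests for secondary endpoints, with modelling where appropriate.
- **Schedule of Activities.** As extracted, the row for these scales is marked at screening and at Visit 3 (POD2), whereas sections 3 and 6.2.2 say POD3.

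**The concern.** The opioid total has a rule for patients who leave before POD3: it stops at discharge. Pain scores start in the PACU, so a patient who goes home early still contributes some values. HADS and PANAS have a single follow-up, tied to being in hospital on POD3, and no rule for those who have left. Their outcome is not shortened; it is absent.

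Whether a patient is still in hospital on POD3 is settled after randomisation and is likely to follow recovery. Section 1.2 itself associates acute pain and cognitive dysfunction with longer stay. Patients without scores are therefore likely to differ from those with scores. Two things are at stake: precision, on endpoints with about 30 patients per arm, and the comparability of the arms if the share discharged early differs between them. These scales carry much of objective C in section 2.1, neuropsychological recovery.

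**Working it through.** **1. The plan's own figure.** The documents give no power or sample-size figure for HADS or PANAS. The only power statement, in section 9.1, is 83% for opioid consumption with 60 patients, means 0.7 and 6.5, SDs 3 and 10, and a two-sided unequal-variance t-test. With 30 per arm and an assumed alpha of 0.05 (not stated):

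- SE = sqrt(9/30 + 100/30) = 1.906
- noncentrality = 5.8/1.906 = 3.04, with 34.2 degrees of freedom
- power = 84%, close to the stated 83%

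Thirty per arm also matches Figure 2 and is used below. Section 9.1 mentions 71 patients as well; the percentages in step 2 do not depend on that choice.

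**2. Precision.** The share discharged before POD3 is an assumption. With a fraction m missing and complete-case analysis, the standard error is multiplied by 1/sqrt(1 − m). The last column is the standardised difference detectable with 80% power by a two-sided 0.05 t-test.

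| Missing | Patients per arm | SE increase | Detectable difference |
|---|---|---|---|
| 0% | 30 | none | 0.74 SD |
| 20% | 24 | 1/sqrt(0.8) = 1.118, so 12% | 0.83 SD |
| 40% | 18 | 1/sqrt(0.6) = 1.291, so 29% | 0.96 SD |
| 60% | 12 | 1/sqrt(0.4) = 1.581, so 58% | 1.20 SD |

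These are complete-case figures. Above 20% the plan calls for imputation, which regains precision only as far as the other variables predict the missing scores.

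**3. Bias between arms.** This is an illustration with assumed inputs. Let recovery be standard normal, let the best-recovered fraction p of an arm leave early, and let recovery correlate rho with the mood score. Among those who remain, mean recovery is lowered by φ(z)/(1 − p), where z is the normal quantile of 1 − p. With no true effect on the score, the spurious difference is rho times the difference in that quantity between arms.

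- p = 30%: 0.3477/0.70 = 0.497
- p = 40%: 0.3863/0.60 = 0.644
- p = 50%: 0.3989/0.50 = 0.798

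Results:

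- 40% v 30%, rho 0.3-0.5: 0.147 × 0.3 = 0.04 to 0.147 × 0.5 = 0.07 SD
- 50% v 30%, rho 0.5-0.7: 0.301 × 0.5 = 0.15 to 0.301 × 0.7 = 0.21 SD
- equal p in both arms: 0

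A simulation of the same type assumed that caffeine shifts recovery by 0.5 SD, that rho is 0.3-0.5, and that 80%, 60% or 40% of placebo patients are still in hospital. The corresponding caffeine shares were 63%, 40% and 23%, and the spurious difference was 0.07-0.18 SD against caffeine. If a true benefit of 0.15-0.25 SD acted wholly through recovery, the inpatient comparison showed only 0.04-0.13 SD. With no shift in recovery the spurious difference was zero.

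**4. The imputation rule.** Baseline scores, pain, opioid use, delirium and sleep up to discharge, and Quality of Recovery on POD1 could all serve as auxiliary variables. If discharge depends only on such recorded values, imputation is valid. If it also depends on unrecorded recovery that is related to mood, it is not, and the observed data cannot tell the two apart.

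**The case against.** The strongest reply is that section 9.2.2 already covers missing scores. A reader might infer from the inpatient-only visit that the arms will be compared only in patients still in hospital, so that randomisation is lost. The documents do not support that: above 20% missing the plan calls for imputation, which keeps all patients, and a useful set of auxiliary variables is recorded before discharge. The reply stands in part. It disposes of the view that a complete-case comparison is fixed, but not of the doubt about MAR, and section 9.2.2 names no sensitivity analysis.

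A reader might also infer that the protocol expects caffeine to shorten stay. It does not say so. Section 1.3 hypothesises effects on opioid consumption, pain and neuropsychological recovery; length of stay is neither hypothesised nor an endpoint. The link from treatment to discharge is an inference from sections 1.2 and 1.3, and without it the between-arm bias in step 3 is about zero. This objection stands in full.

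The bias figures are modest. With 15 and 21 patients remaining, 0.15 SD is 0.15/sqrt(1/15 + 1/21) = 0.15/0.338 = 0.45 standard errors. Two of the three endpoints are binary screens (score 8 or more), to which an SD bias does not translate directly.

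Lastly, no sentence says that discharged patients are skipped, and staff might give the scales at discharge. But both sections that set the timing fix it at POD3, section 3 with the words "after the last inpatient assessment on postoperative day 3", and no alternative is written down.

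**Conclusion.** The point holds as a gap in data collection. Followed as written, the plan leaves three of eight secondary endpoints without follow-up scores for patients who leave before POD3, through a post-randomisation event plausibly related to recovery. Imputation reduces the harm but rests on an assumption that is doubtful here.

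The size cannot be fixed from the documents, because neither length of stay nor the share discharged early is given. The 12-58% rise in standard errors assumes 20-60% missing and complete-case analysis. Bias of roughly 0.04-0.2 SD further assumes that early discharge differs by arm and that recovery correlates with mood. Without a difference in discharge the loss is one of precision, and a complete-case result would describe longer-stay patients only. If few leave early, the whole matter is small.

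These are secondary endpoints in a Phase II trial with a feasibility objective, so the change is advisable and does not threaten the primary analysis.

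**What to change.** - **Collection.** Obtain follow-up HADS and PANAS from every randomised patient. For those already discharged, give both by telephone on the target day; failing that, at the first scheduled POD4-7 call.
- **Recording and reporting.** Record mode and day of each assessment, and report completion by arm and discharge status.
- **Analysis.** Analyse all randomised patients. For scores still missing, name the auxiliary variables for imputation. Add a sensitivity analysis for mode, timing and departures from MAR, for example by shifting imputed scores by stated amounts in each arm.
- **Timing.** Reconcile the Schedule of Activities, which as extracted appears to mark these scales at POD2, with the POD3 timing in sections 3 and 6.2.2. This may be a table-reading effect or a confusion between study day 3 and POD3, but the day determines how many patients have already left.

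**Cost.** A POD3 call is a short new contact for some patients, since the scheduled calls begin on POD4. Mode, setting and possibly day will then depend on discharge status, so if discharge differs by arm, measurement conditions differ too. Recording them does not remove that difference, but lets it be examined. Calling on the target day keeps it smallest.
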